
Resources:

Space. The research methodology described in this application will primarily be conducted in the Biodynamics Laboratory. Patient care and rehabilitation will be provided in Mayo Clinic Sports Medicine Centers (SMCs).

Mayo Clinic has recently built two state of the art outpatient Sports Medicine Centers (SMCs) in Rochester and Minneapolis, MN. The offices and facilities of the SMCs are dedicated to creating an atmosphere of clinical, research and academic excellence. All facilities and resources are readily available to [name], and include everything necessary for the successful completion of this proposal. The availability of two sports medicine rehabilitation centers within the Mayo Clinic system that provide standardized care enhances the ability to provide patient services to a large geographic region. Both clinics occupy more than 20,000 square feet. Eleven physical therapists, seven athletic trainers, and three performance coaches provide rehabilitation services. Physician treatment rooms are housed on the same floor at each site. Five sports medicine, fellowship-trained physicians comprise the surgical team, including [name] (PI). All of the surgery providers are participating in the investigation.

This project will utilize the dual clinical spaces available at Mayo Clinic Sports Medicine housed within the Dan Abraham Healthy Living Center (DAHLC) in Rochester, MN, as well as Mayo Clinic Square in downtown Minneapolis, MN. The DAHLC houses approximately 25,000 square feet of clinical sports medicine treatment space, which includes exam rooms, radiology suite with access to MRI, strength and mobility training equipment, an enclosed turf field, reception area, open office space for staff that is in close proximity to the clinical treatment space. In addition, there is another approximately 13,000 feet of clinical sports medicine space housed in the Charlton Building for a total of approximately 38,000 feet of clinical treatment space in Rochester, MN. Mayo Clinic Square is comprised of approximately 25,000 square feet of clinical sports medicine treatment space, which includes exam rooms, radiology suite with access to MRI, strength and mobility training equipment, isokinetic/isometric dynamometers, an enclosed turf field, reception area, open office space for staff that is in close proximity to the clinical treatment space. These state of the art facilities will be the site of patient care and rehabilitation following ACL reconstruction surgery.

The Biodynamics Laboratory is located within the SMC in Minneapolis, MN. It contains approximately 1,800 square feet dedicated to the latest state-of-the art, cutting edge technology motion capture and neuromuscular control assessment currently available.

Equipment.

1. 14 Camera Motion Analysis System (Raptor Cameras, Motion Analysis Corp., Santa Rosa, CA) with assorted height mounting rails and 14 mounting brackets for flexible camera placement (Figure FE1).
2. Cortex software (v3, Motion Analysis Corp., Santa Rosa, CA) including Skelton Builder, Calcium, BioFeedTrak, and Kintools RT.
3. Four (4) 60 x 90 centimeter, 6-component force plates (Bertec, Columbus, OH)
4. Motion analysis data acquisition computer workstation: Dell Precision T7500, 6-core Xeon X5690 3.47 GHz CPU, 12 GB ECC RAM, 3 Hitachi 15k SAS hard drives (250GB boot drive and 2x 500GB drives in a RAID 0 array), dual Nvidia Quadro 2000 video cards, and 3 30" Dell monitors, Windows 7. UPS battery backup on all motion capture equipment.

5. Three (3) Microsoft Lifecam Studio HD webcams (Higher quality cameras are needed for this study, please see the budget justification for the proposed make and model of purchase)
6. One (1) static digitizing probe for creating calibration marker locations on hard-to-reach anatomical landmarks.
7. Two (2) Visual 3D motion analysis software licenses (C-motion inc., Germantown, MD)
8. Two (2) Microsoft Kinect 3D cameras (Microsoft Corp., Redmond, WA)
9. Two (2) Wii Balance boards (Nintendo of America, Inc., Redmond, WA)
10. Two HumacNORM isokinetic and isometric dynamometers with accompanying software (Figure FE2, CSMi, Stoughton, MA).
11. Two Humac balance devices with accompanying software (CSMi, Stoughton, MA).
12. One GNRB arthrometer (Genourob, Laval, France)
13. Two (2) complete Simi Aktisys marker-based and marker-less motion analysis systems with associated cameras, hardware, and software (Simi Reality Motion Systems GmbH, Unterschleissheim, Germany).
14. Thirteen (13) Dartfish Motion Pro Premium licenses with fourteen (14) associated cameras and necessary hardware split between Mayo Clinic Rochester and Mayo Clinic Square facilities (Dartfish USA, Inc., Alpharetta, GA).

Computer/Office

Adequate dedicated office space and computing capabilities already exists within the laboratories and clinical facilities to meet the needs of all personnel included in this project. Each listed clinical and laboratory space also has designated multimedia conference room space with teleconferencing capabilities. All key personnel have office space in both Minneapolis and Rochester SMCs.

(1a) This is a multisite study involving Mayo Clinic and non Mayo Clinic sites. *When checked, describe in detail the research procedures or activities that will be conducted by Mayo Clinic study staff.*

(1b) Mayo Clinic study staff will be engaged in research activity at a non Mayo Clinic site. *When checked, provide a detailed description of the activity that will be conducted by Mayo Clinic study staff.*

Subject Information

Target accrual: This study will enroll 150 subjects. Anticipating a 30% dropout rate, this will yield a final accrual of 120 subjects.

Subject population (children, adults, groups): All subjects will be patients who undergo primary ACL reconstruction, and will be recruited from the practices of the sports medicine surgical team at Mayo Clinic, Rochester, MN, as well as the practices of the surgeon affiliates of the sports medicine team at Cincinnati Children's Hospital Medical Center, Cincinnati, OH. Recruitment will also include primary ACL reconstruction patients from the sports medicine surgical team at the University of Minnesota, Minneapolis, MN, and primary ACL reconstruction patients from the sports medicine surgical team at Mayo Clinic Health System, La Crosse, WI. This will include male and female patients between the ages of 13 and 30 years in age

at the time of injury. The University of Minnesota and Mayo Health System locations will serve only as referral sites as no research activity will occur there.

Inclusion Criteria:

1. Age, 13 \geq 30 years, 2. Acute, first-time, isolated ACL injury, 3. No history of previous knee surgery to either extremity, 4. No low back or lower extremity injury in the year prior to ACL injury necessitating medical care, 5. Pre-injury participation in cutting, jumping or pivoting sports for \geq 50 hours/year, 6. Plan to return to full participation in sports following ACL reconstruction.
7. Mechanism of injury did not involve a direct blow to the knee

Patients who sustain a medial collateral ligament (MCL) injury are eligible for study participation if medial knee instability is resolved prior to surgery.

This age range is selected secondary to the majority of ACL injuries occurring in young, active individuals who participate in jumping, cutting and pivoting sports on a regular basis.

Patients with simple meniscus tears (i.e., 2 cm vertical longitudinal tear) that do not necessitate alterations in rehabilitation will be eligible for study participation.

Exclusion Criteria:

Patients with complex, repairable meniscus tears (i.e., radial or root repair), multi-ligament repair, and patients with full thickness articular cartilage lesions will not be eligible for participation.

Research Activity

Check all that apply and complete the appropriate sections as instructed.

1. **Drug & Device:** Drugs for which an investigational new drug application is not required. Device for which (i) an investigational device exemption application is not required; or the medical device is cleared/approved for marketing and being used in accordance with its cleared/approved labeling. (Specify in the Methods section)
2. **Blood:** Collection of blood samples by finger stick, heel stick, ear stick, or venipuncture.
3. **Biological specimens other than blood:** Prospective collection of human biological specimens by noninvasive means that may include: urine, sweat, saliva, buccal scraping, oral/anal/vaginal swab, sputum, hair and nail clippings, etc.
4. **Tests & Procedures:** Collection of data through noninvasive tests and procedures routinely employed in clinical practice that may include: MRI, surface EEG, echo, ultrasound, moderate exercise, muscular strength & flexibility testing, biometrics, cognition testing, eye exam, etc. (Specify in the Methods section)

5. **Data** (medical record, images, or specimens): Research involving use of existing and/or prospectively collected data.
6. **Digital Record**: Collection of electronic data from voice, video, digital, or image recording. (Specify in the Methods section)
7. **Survey, Interview, Focus Group**: Research on individual or group characteristics or behavior, survey, interview, oral history, focus group, program evaluation, etc. (Specify in the Methods section)

NIH has issued a *Certificate of Confidentiality* (COC). *When checked, provide the institution and investigator named on the COC and explain why one was requested.* _____

Biospecimens – Categories 2 and 3

(2) Collection of blood samples. When multiple groups are involved copy and paste the appropriate section below for example repeat section b when drawing blood from children and adults with cancer.

- a. **From healthy, non-pregnant, adult subjects who weigh at least 110 pounds.** For a minimal risk application, the amount of blood drawn from these subjects may not exceed 550ml in an 8 week period and collection may not occur more frequently than 2 times per week.

Volume per blood draw: _____ ml

Frequency of blood draw (e.g. single draw, time(s) per week, per year, etc.) _____

- b. **From other adults and children considering age, weight, and health of subject.** For a minimal risk application, the amount of blood drawn from these subjects may not exceed the lesser of 50 ml or 3 ml per kg in an 8 week period, and collection may not occur more frequently than 2 times per week.

Volume per blood draw: _____ ml

Frequency of blood draw (e.g. single draw, time(s) per week, per year, etc.) _____

(3) Prospective collection of biological specimens other than blood: _____

Review of medical records, images, specimens – Category 5

For review of existing data: provide a date range or an end date for when the data was generated. The end date can be the date this application was submitted to the IRB. Example: 01/01/1999 to 12/31/2015 or all records through mm/dd/yyyy.

Date Range:

Check all that apply (data includes medical records, images, specimens).

(5a) Only data that exists before the IRB submission date will be collected.

(5b) The study involves data that exist at the time of IRB submission **and** data that will be generated after IRB submission. Include this activity in the Methods section.

Examples

- The study plans to conduct a retrospective chart review and ask subjects to complete a questionnaire.
- The study plans to include subjects previously diagnosed with a specific disease and add newly diagnosed subjects in the future.

(5c) The study will use data that have been collected under another IRB protocol. Include in the Methods section and enter the IRB number from which the research material will be obtained. *When appropriate, note when subjects have provided consent for future use of their data and/or specimens as described in this protocol.*

Enter one IRB number per line, add more lines as needed

Data Specimens Data & Specimens _____

Data Specimens Data & Specimens _____

Data Specimens Data & Specimens _____

(5d) This study will obtain data generated from other sources. Examples may include receiving data from participating sites or an external collaborator, accessing an external database or registry, etc. Explain the source and how the data will be used in the Methods section.

(6) Video audio recording: *Describe the plan to maintain subject privacy and data confidentiality, transcription, store or destroy, etc.*

Files will be stored on a secured server to which only authorized study personnel may access. Files will be named according to the subject's research study ID. Files will be used for research analysis only and not distributed.

HIPAA Identifiers and Protected Health Information (PHI)

Protected health information is medical data that can be linked to the subject directly or through a combination of indirect identifiers.

Recording identifiers (including a code) during the conduct of the study allows you to return to the medical record or data source to delete duplicate subjects, check a missing or questionable entry, add new data points, etc. De-identified data is medical information that has been stripped of all HIPAA identifiers so that it cannot be linked back to the subject. De-identified data is **rarely** used in the conduct of a research study involving a chart review.

Review the list of subject identifiers below and, if applicable, check the box next to each HIPAA identifier being recorded at the time of data collection or abstraction. Identifiers apply to any subject enrolled in the study including Mayo Clinic staff, patients and their relatives and household members.

Internal refers to the subject's identifier that will be recorded at Mayo Clinic by the study staff.

External refers to the subject's identifier that will be shared outside of Mayo Clinic.

Check all that apply:	INTERNAL	EXTERNAL
Name		
Mayo Clinic medical record or patient registration number, lab accession, specimen or radiologic image number	X	
Subject ID, subject code or any other person-specific unique identifying number, characteristic or code that can link the subject to their medical data	X	
Dates: All elements of dates [month, day, and year] directly related to an individual, their birth date, date of death, date of diagnosis, etc. Note: Recording a year only is not a unique identifier.	X	
Social Security number		
Medical device identifiers and serial numbers		
Biometric identifiers, including finger and voice prints, full face photographic images and any comparable images	X	
Web Universal Resource Locators (URLs), Internet Protocol (IP) address numbers, email address	X	
Street address, city, county, precinct, zip code, and their equivalent geocodes	X	
Phone or fax numbers	X	
Account, member, certificate or professional license numbers, health beneficiary numbers		
Vehicle identifiers and serial numbers, including license plate numbers		
Check 'None' when none of the identifiers listed above will be recorded, maintained, or shared during the conduct of this study. (exempt category 4)	 None	 None

Data Analysis

Power analyses and study endpoints are not required for minimal risk research, pilot or feasibility studies.

No statistical information. *If checked, please explain:*

Power Statement:

We expect that the minimal clinically significant effect size of TNMT on knee biomechanics is 0.17 or above. Using an a priori power analysis based on repeated measures ANOVA, we expect that to achieve 80% power with $\alpha = 0.05$, this study will require a final accrual of 87 subjects. This assumes a correlation coefficient of 0.3 among the repeated measures, which is likely conservative. Thus, an accrual of 116 (with an estimated 30% dropout rate) subjects will be sufficient to determine if a clinically significant reduction in unininvolved limb transverse plane hip net moment impulse, frontal plane knee joint ROM, initial contact sagittal plane knee moment asymmetry, and deficits of involved limb postural stability has occurred as a result of TNMT. This sample size provides adequate power for all variables of interest for Aims 1 and 2. Mayo Clinic averages more than 120 ACLR per year in the Minneapolis/Rochester region on individuals under age 25. Thus, the available patient pool is more than adequate to meet study requirements.

Data Analysis Plan:

Aim 1: We will utilize normal mixture based clustering analysis⁷⁰ to identify groups with distinguished risks based on a priori covariates (i.e., demographics and biomechanical variables). Our previous work used a similar approach to effectively cluster subjects into three distinct risk groups. We intend to confirm disparate risk for injury by assessment of the magnitude of differences across groups using knee and hip abduction angles, surrogates for ACL injury.

The normal mixture model approach works by assuming the density of the covariates for a subject x , can be described as:

$$f(x) = \sum_{k=1}^K \pi_k \phi(x; \mu_k, \Sigma_k),$$

where (i) K is the number of mixture components (groups), (ii) π_k is the unconditional probability that a subject fall into the k th group, and (iii) $\phi(\cdot; \mu, \Sigma)$ is the multivariate normal density with mean μ and covariance Σ . Estimates of the parameters, π_k, μ_k, Σ_k , are typically obtained using maximum likelihood. The number of groups is most commonly chosen to optimize the Bayesian Information Criterion (BIC). Often assumptions such as a common covariance matrix for all k , or common shape (i.e., correlation) matrix, are made to make estimation feasible, depending on the size of data, and these decisions are also commonly made on the basis of BIC. In this work we intend to assume a common Σ , and assess the validity of this assumption via model diagnostics. Once parameter estimates are obtained, clustering is performed by calculating the probability of group membership m for a given subject, conditional on his/her covariate values, i.e.,

$$P(m = k | x) = \frac{\pi_k \phi(x; \mu_k, \Sigma_k)}{\sum_{l=1}^K \pi_l \phi(x; \mu_l, \Sigma_l)}.$$

The subject will then be assigned to the group k that results in the largest conditional group membership probability $P(m = k | x)$. This approach has been shown to perform very well in the presence of a large number of variables with the inclusion of a variable selection mechanism.^{71, 72} We will leverage such an approach in our analysis to identify a reduced set of biomechanical variables that most informatively differentiate the subjects.

Aim 2:

Aim 2 will utilize a prospective, single blind, randomized clinical trial design. Subjects from Aim 1 will comprise the study sample. Subjects will undergo testing twice.

We will use a repeated-measures ANOVA model with between-subjects factors that include interactions, to determine the effect of TNMT compared to HOME or STAN treatment on clinical performance after ACLR. Specifically, for a response of interest y , e.g., hip abductor strength, for the i^{th} subject in the k^{th} treatment group, with $l = 0$ indicating before intervention and $l = 1$ indicating after,

$$y_{ikl} = \alpha + \delta_l + (\gamma\delta)_{kl} + \tau_{i(k)} + \epsilon_{ikl}$$

with (i) intercept α , (ii) subject random effect $\tau_{i(jk)} \sim N(0, \sigma_{\alpha}^2)$, (iii) pure error (or noise) $\epsilon_{ijk1} \sim N(0, \sigma_{\epsilon}^2)$, (iv) δ_l is the main effect due to intervention, and (vi) $(\gamma\delta)_{kl}$ is the interaction effect allowing intervention efficacy to vary with intervention type. The fixed effects are constrained such that $\delta_0 = (\gamma\delta)_{k0} = 0$. In this model, the baseline (i.e., pre-treatment) response for an individual is:

$$y_{ikl} = \alpha + \tau_{i(k)} + \epsilon_{ikl}.$$

Thus, the pre- intervention response for a given subject is the same regardless of which intervention group k they were assigned to, since nothing would have happened yet within their intervention group to distinguish them from other groups. Under the formulation in (1), the difference between observations before and after intervention is:

$$d_{ijk} = y_{ijk1} - y_{ijk0} = \delta^* + \gamma_k^* + \epsilon_{ijk}^*$$

where $\delta^* = \delta_1$, $\gamma_k^* = (\gamma\delta)_{k1}$, and $\epsilon_{ijk}^* = (\epsilon_{ijk1} - \epsilon_{ijk0}) \sim N(0, 2\sigma_{\epsilon}^2)$. The primary inference of interest is with respect to the relative efficacy of rehabilitation type γ_k^* and the effect of risk group on intervention efficacy, along with their interaction $(\beta\gamma)_{jk}^*$. Thus, this inference could equivalently be conducted using the pairwise differences in a straightforward one-way ANOVA model. We will assess model assumptions (e.g., normality and constant variance) via residual diagnostics and apply transformations if needed. Where appropriate, we will also utilize Tukey HSD post hoc analysis to further determine significance between groups on intervention effect.

Endpoints

There will be no known direct medical benefits to subjects from participating in this study.

Primary: Completion of all study activities

Secondary: Second injury

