Overall Strategy. This is a prospective, randomized, repeated measures single- blind clinical trial. The purposes of this study are to 1) stratify patient risk for second ACL injury, and 2) determine the effects of differential treatment intervention, including targeted neuromuscular training (TNMT), home program only (HOME) and standard clinical (STAN) training, on clinical, biomechanical, and neuromuscular performance measures associated with an increased secondary ACL injury risk. At this time there is no evidence to support one intervention as either superior or inferior to the other interventions proposed in this study. After the initial ACL injury and study enrollment, all patients will participate in standardized pre-operative rehabilitation. They will then undergo surgery by a fellowship-trained sports medicine surgeon at Mayo Clinic, Rochester, MN. Data for Aim 1 will be obtained from biomechanical, neuromuscular and clinical testing performed during Pre-Testing. Data for Aim 2 and the Exploratory Aim will be obtained from biomechanical and clinical test results obtained from Pre- and Post-Testing time points.

Common Rehabilitation. All study participants will follow the same rehabilitation guidelines before and immediately after surgery, until they are cleared by their attending surgeon to return to full participation in sports. After clearance, they will be randomized into the differential treatment groups. Entry into this phase is criteria-based, and represents the standards identified in the literature for entry into the final phase of rehabilitation. These criteria include: symmetrical knee range of motion; minimal or no pain and knee effusion; quadriceps strength $\geq 80\%$ compared to contralateral limb (180°/sec and 300°/sec); self-report of function $\geq 80\%$; limb symmetry index during single leg hop for distance $\geq 80\%$. Both pre- and postoperative rehabilitation protocols are a composite of previously published, evidence-based protocols from expert researchers and clinicians.⁶⁵⁻⁶⁷

Differential Rehabilitation. Once study participants are cleared for full participation in sports, they will be randomized into one of three groups for differential treatment. This will include HOME, STAN and TNMT

groups. If patient lives at a distance from Mayo Clinic and cannot participate in the weekly training but is able to come to both testing session they will be randomized into the HOME and STAN programs.

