HOME Program is distinguished by patients participating in a home only intervention that consists of running exercises performed twice a week for six to eight weeks. No plyometric or agility drills are performed in this study arm. This represents the minimal intervention to prepare for a return to sports. No neuromuscular training or movement training beyond the sagittal plane will be performed.

Patients in the STAN group will be used as the control group. They will receive no training. They will participate in the two testing sessions and the weekly survey updates.

Patients who are enrolled in the TNMT group will participate in 12 sessions of supervised outpatient physical therapy over a six to eight week period. The TNMT protocol is distinguished by performance of exercises designed to enhance core and hip strength, performance of neuromuscular training exercise that are designed to correct movement flaws associated with second ACL injury²⁵, providing verbal and visual feedback and performance of single leg drills on both legs.

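### At the stated 30% dropout, 150 enrolled leaves 105 completers rather than 120, and the accrual of 116 leaves 81, short of the plan's own requirement of 87

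*Combined protocol and SAP*

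**What the plan says.** Two places apply a dropout rate.

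- Subject Information, Target accrual: "This study will enroll 150 subjects. Anticipating a 30% dropout rate, this will yield a final accrual of 120 subjects".
- Data Analysis, Power Statement: for 80% power at alpha 0.05 and an effect size of 0.17, "this study will require a final accrual of 87 subjects". On dropout it adds that "an accrual of 116 (with an estimated 30% dropout rate) subjects will be sufficient". On correlation: "This assumes a correlation coefficient of 0.3 among the repeated measures, which is likely conservative".

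The Power Statement names repeated-measures ANOVA. It does not name the effect-size metric, the term tested, the number of measurements or the allocation.

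The design is described elsewhere. There are three randomized groups (Differential Rehabilitation), and the same section restricts patients who live too far away for weekly training to HOME or STAN. Aim 2 data come from "clinical test results obtained from Pre- and Post-Testing time points", and the Data Analysis Plan for Aim 2 says "Subjects will undergo testing twice".

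That plan displays a model with a random subject effect, a time effect and an arm-by-time effect, and with the same baseline mean in every arm. It states that "The primary inference of interest is with respect to the relative efficacy of rehabilitation type", together with risk group and an interaction. It then says that the inference could equivalently be made by a one-way ANOVA on the before-after differences.

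**The concern.** Both places carry the same 30% label, yet the figures imply two different rates, and neither is 30%. In Subject Information the expected number of completers is overstated. In the Power Statement the direction is the reverse: 87 is the requirement and 116 is derived from it, so the error lies in the accrual or in the rate. On the plan's own terms, 116 enrolled at 30% loss is not sufficient.

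Retention would be planned and judged against 120 completers, a number that the stated rate cannot deliver. Once the count is corrected to 105, the natural next question is what power 105 gives. The plan does not supply enough to answer it.

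**Working it through.** **1. Dropout arithmetic (documents only, no assumptions).** Completers = enrolled × (1 − rate); enrolled = completers / (1 − rate), rounded up.

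- Subject Information: 150 × 0.70 = 105, not 120. Implied rate: 1 − 120/150 = 20%.
- Power Statement: 116 × 0.70 = 81.2, so 81, not 87. Implied rate: 1 − 87/116 = 25%. At 30%, 87/0.70 = 124.3, so 125 enrolled.
- Multiplying by 1.3 instead of dividing by 0.7 does not explain the figures either: 87 × 1.3 = 113.1 and 120 × 1.3 = 156, against 116 and 150.

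Applying one rate to both statements gives:

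| Rate | 150 enrolled leaves | 87 completers need |
|---|---|---|
| 30% | 105 | 125 |
| 25% | 112 (112.5) | 116 |
| 20% | 120 | 109 (108.75) |

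No single rate gives both 120 and 116.

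**2. Attempt to reproduce 87.** From the plan: effect size 0.17, alpha 0.05, power 80%, correlation ρ = 0.3, k = 3 groups, m = 2 tests. Assumed: the metric is Cohen's f, arms are equal, the test is arm-by-time, and there is no multiplicity adjustment. Noncentral F with λ = f²·N·m/(1 − ρ), df (k − 1)(m − 1) and (N − k)(m − 1).

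- N = 87: λ = 0.0289 × 87 × 2/0.7 = 7.18, power 65.1%.
- N = 105: λ = 8.67, power 74.1%.
- N = 120: λ = 9.91, power 80.1%. This is the smallest N that reaches 80%.

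So 87 is not reproduced under these assumptions. It does appear with two tests at ρ = 0.5 (80.3%). It also appears at ρ = 0.3 with four measurements (minimum 85, or 87 with equal arms). The first differs from the stated correlation, the second from the two test sessions described.

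**3. Range at 105 completers, arm-by-time test.**

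| ρ | 0.2 | 0.3 | 0.4 | 0.5 | 0.6 |
|---|---|---|---|---|---|
| Power | 68% | 74% | 81% | 88% | 94% |

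Power reaches 80% at ρ of about 0.39.

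Unequal arms: suppose TNMT alone differs, by the amount that gives f = 0.17 with equal arms. With ρ = 0.3 and 105 completers, power falls from 74% to about 66% if TNMT holds 25% of completers, and to about 59% if it holds 20%.

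**4. Does the Aim 2 analysis matter?** It depends on how the displayed model is fitted.

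- As a conventional repeated-measures ANOVA with within-subject error, the arm-by-time F is identical to the one-way ANOVA F on differences. The plan's statement of equivalence holds, and the figures in steps 2 and 3 apply.
- Fitted by likelihood or generalized least squares with the random subject effect and common baseline, the model also uses the baseline information. Then λ = 4f²N/(1 − ρ²), df 2 and N − 4. At N = 105 and ρ = 0.3, λ = 4 × 0.0289 × 105/0.91 = 13.34, power 90.7%. The minimum N is 79.

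Simulation at 105 completers and ρ = 0.3 agrees: 74.2% for differences and 90.5% for the likelihood fit.

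**The case against.** The strongest reply is that nothing in the conclusion changes. The target is 150, which leaves 105 even at 30%, and 105 exceeds 87. The form itself says that power analyses are not required for minimal risk research, and the listed primary endpoint is completion of study activities. The plan also calls 0.3 conservative, and a higher correlation would raise power. Most of this stands, and it limits the point to a correction of stated figures. It does not excuse them: the sponsor chose to give a power statement, claims adequate power for Aims 1 and 2 from it, and the sums are wrong on their face.

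Three stronger readings are tempting, and the documents do not support them.

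- A reader might infer that the trial is underpowered. The 74% rests on an assumed metric, equal arms and the stated 0.3. At 0.5 it is 88%, and under a likelihood fit about 91%.
- A reader might infer that 87 is an error. The inputs are missing, so its origin is undetermined. The Aim 2 model is introduced for clinical performance while the Power Statement concerns knee biomechanics, so four measurements cannot be ruled out on that model alone.
- A reader might infer that the plan is simply wrong to call the two Aim 2 analyses equivalent. For a conventional repeated-measures ANOVA it is right. The statement fails only under likelihood or generalized least squares fitting, which the plan does not specify for Aim 2.

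**Conclusion.** The dropout figures are wrong as written and must be corrected. This rests on the documents alone. The expected completers from 150 are overstated by 15 (105 against 120). The accrual of 116 falls 6 completers short of its own requirement (81 against 87), or 9 enrolled short of the 125 that it would need.

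The rest is secondary and conditional. Under the assumptions in the working, 105 completers give about 74% power by the arm-by-time test at correlation 0.3, less if TNMT is the smaller arm and more if a higher correlation is justified. The allocation caveat is a real one, since the plan sends distant patients only to HOME or STAN. A likelihood fit of the displayed model would give about 91%. What is established is that the plan does not let a reader determine its power at the corrected count, not that the power is inadequate.

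**What to change.** **Must change.** Use one enrolment target and one dropout rate in Subject Information and in the Power Statement, and restate what they imply. For 150: 105 completers at 30%, or a rate of 20% if 120 is meant. For 87: 125 enrolled at 30%, or a rate of 25% if 116 stands. Because 20% and 25% cannot both be the single rate, at least one of the figures 120 and 116 has to change.

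**Should be added.** State the effect-size metric, tested term, number of measurements, allocation (including the effect of the HOME/STAN restriction) and correlation behind 87. Name one Aim 2 analysis and its fitting method, and restate power at the corrected completer count. Limit the statement of equivalence to the fitting method for which it holds.

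**Cost.** Wording only; no extra patients are needed to correct the figures. The downside is a less favourable stated completer count, and possibly a lower stated power. Enrolment would come into question only if the sponsor chose the ANOVA on differences, kept correlation 0.3 and 30% dropout, and still wanted 80% under the assumptions above: 120/0.70 = 171.4, so 172 enrolled.
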